# 6.2. Exclusion Criteria

Subjects will be excluded if any of the following exclusion criteria are met:

- 1. Has a history of any severe anaphylactic reaction to blood or any blood-derived product.
- 2. Has selective IgA deficiency or has a history of antibodies to IgA.
- 3. Has clinically significant impairment of cellular or innate immunity at the discretion of the Investigator.
- 4. Has evidence of an active infection at the time of enrolment (i.e. on day of first infusion). Subjects who are asymptomatic but have not completed their course of antibiotics are eligible.
- 5. Has previously completed or withdrawn from this study.
- 6. Is currently receiving, or has received, any investigational agent within the prior three months unless it is an investigational stage III, IIIb IGIV or SCIG.
- 7. Is pregnant (confirmed by a positive result on an HCG-based pregnancy test) or is nursing.
- 8. Is positive for any of the following at screening:

Page 19 of 87

- Serological test for HIV 1&2, HCV, or HBsAg
- 9. Has levels at screening greater than 2.5 times the upper limit of normal as defined at the central laboratory of any of the following:
  - Alanine transaminase (ALT)
  - Aspartate transaminase (AST)
- 10. Has severe renal impairment (defined as serum creatinine greater than two times the upper limit of normal or BUN greater than two times the upper limit of normal for the range of the laboratory doing the analysis); the subject is on dialysis or has a history of acute renal failure.
- 11. Is known to abuse alcohol, opiates, psychotropic agents, or other chemicals or drugs, or has done so within the past 12 months.
- 12. Has a history of DVT, or thrombotic complications of immunoglobulin therapy, or a diagnosis of thrombophilia.
- 13. Suffers from any acute or chronic medical condition (e.g. renal disease or predisposing conditions for renal disease, coronary artery disease, or protein losing state, proteinuria) that the Investigator feels may interfere with the conduct of the study.
- 14. Has an acquired medical condition, such as chronic lymphocytic leukemia, lymphoma, multiple myeloma, chronic or recurrent neutropenia (ANC  $< 1 \times 10^9$ /L).
- 15. Is receiving the following medication:
  - Steroids (long-term daily, ≥ 0.15 mg of prednisone equivalent/kg/day). Requirement for short or intermittent courses of > 0.15mg/kg/day would not exclude a subject.
  - Immunosuppressive drugs
  - Immunomodulatory drugs
- 16. If  $\geq$  18 years of age, has non-controlled arterial hypertension (systolic blood pressure > 160 mmHg and/or diastolic blood pressure > 100 mmHg). For younger subjects refer to current guidelines for diagnosis of blood pressure .
- 17. Has anemia (hemoglobin < 10 g/dL) at screening.
- 18. Has severe dermatitis that would preclude sites for safe product administration.
- 1. The Fourth Report on the Diagnosis, Evaluation, and Treatment of High Blood Pressure in Children and Adolescents. Pediatrics 2004 Aug;114 (Suppl 2:) 555-76.

## 7. STUDY DESIGN AND PLAN

This will be a Phase III, multicenter, open-label, non-randomized study. Up to 50 subjects will be enrolled to ensure 30 evaluable subjects. At least 18 subjects will be adults (aged 16-75 years) and 12 will be children split between the age groups 2 to 5 years (i.e. not reached their 6th birthday), 6 to 11 years (i.e. not reached their 12th birthday) and 12 to 15 years (i.e. not reached their 16th birthday), with a minimum of 4 in each age group.

All children who receive at least one infusion of Subgam-VF will be included in the safety analysis. Due to the potential for early withdrawals, PK data may not be available on all 12 children and there may be fewer than 12 evaluable children in the PK analysis. The total number of subjects (adults plus children) evaluable for PK analysis will be at least 30.

Subjects will receive 26 infusions (weeks) of Subgam-VF at a weekly dose equivalent to 1.37 of their IGIV dose (expressed as mg/kg/week). If the subject was already receiving a weekly SCIG IgG there will be no dose adjustment. Pharmacokinetics and safety of Subgam-VF will be assessed.

All subjects will undergo a pharmacokinetic (PK) profile after the 21st infusion of Subgam-VF (see PK Assessment Schedule, Table 3). Where an appropriately qualified member of the study team is available, arrangements will be made to collect the PK samples from Steady State Day 1 (24 hours post-infusion) onwards at the subject's home to reduce the number of visits to the sites. Alternatively a Home Health Agency may be utilized to take the PK samples outside of the investigational site. The subject would be required to sign an extra IRB/EC approved consent form to permit the site to share the subject's details with the agency in order for them to collect the sample.

In the case of younger children it is important not to exceed the maximum blood withdrawal volumes stated in Appendix V. Therefore smaller volumes of blood will be taken. See the Laboratory Manual for details.

- Following a screening period, eligible subjects will commence weekly Subgam-VF treatment; this is a 16% subcutaneous IgG product.
- Subjects will receive Subgam-VF for 26 weeks during which time safety will be assessed

 The definition of an adult as  $\geq$  16 years is as per the FDA guidance for PK studies. Note this does not affect the requirements for consent/assent, for which each site should follow their IRB guidelines.

- After Week 21, PK sampling will commence to measure  $AUC_{(0-\tau)}$  over 7 days.
- The patient populations will be as similar as possible to that of the historical studies (GMX01 and GMX04) as per similar inclusion/exclusion criteria.
- Comparable methods will be used to determine PK concentrations to that of the historical studies and the AUC measured will be at steady state.
- Follow-up visit Week 27 (one week after the last Subgam-VF infusion).
- Follow-up telephone call Week 30 (four weeks after the last Subgam-VF infusion).
- The initial weekly dose of Subgam-VF administered will be calculated by taking the average weekly equivalent of the subject's IGIV dose (should be stable, as in same mg/kg +/- 5%), multiplied by 1.37, a dose adjustment coefficient based on historical data for other subcutaneous IgG products. If the subject was already receiving a weekly SCIG IgG there will be no dose adjustment.
- Oral and parenteral steroids as concomitant medication are allowed if the average daily dose is < 0.15 mg prednisone equivalent/kg body weight per day. Short or intermittent courses of > 0.15 mg/kg/day are allowed if required.
- Routine premedication to reduce potential adverse effects associated with SCIG infusion are discouraged. Exceptions:
  - Premedication will be permitted if a subject has reported systemic adverse events on two Subgam-VF infusions.
  - Local anesthetics (e.g. an analgesic cream) can be used before any Subgam-VF infusion to reduce the potential pain associated with needle insertion if required.
- Subgam-VF will be administered subcutaneously using infusion pumps.
- Subjects will be given diaries to record adverse event data as well as any infusions administered at home.

## 7.1. Study Visits

For details of which procedure will be performed at any specific visit, see the schedule of assessments (Table 2) in Appendix IV.

## Screening/Baseline

After informed consent/assent (as appropriate):

• Screening/baseline – subjects receive their usual dose of IGIV/SCIG and have all safety screening tests performed, including biochemistry, hematology, virology, vital signs and serum IgG trough levels.

# **Treatment Period (Weeks 1 to 26)**

• Eligible subjects then return seven days (+/- 1 day) after the Screening/Baseline visit for their first Subgam-VF dose (Week 1 visit). Weekly dosing will be administered for 26 weeks during which time safety will be assessed. Site visits (Weeks 1, 2, 5, 9,

Page 22 of 87

13, 17, 21, 22 and 26) – subjects will attend the clinic at specific points and they will receive their Subgam-VF infusion at the clinic. There will also be routine safety assessments, which will include blood sampling. After the Week 2 visit and if an appropriately qualified member of the study team or the subject's carer is available, then arrangements may be made to conduct some of the visits at the subject's home to reduce the number of visits to the sites. Alternatively a Home Health Agency may be utilized. The subject would be required to sign an IRB/EC approved consent form to permit the site to share the subject's details with the agency in order for them to collect the samples/conduct the assessments.

- If the subject is not already receiving IgG via the subcutaneous route, following training by the site during the preceding Subgam-VF visits it is planned that home infusions will begin on Week 3 (3rd infusion of Subgam-VF). For home infusions, subjects (or care givers) will infuse Subgam-VF themselves and will record any concomitant medications, date and time of any adverse events (including inspecting the infusion site for reactions) and record details of their Subgam-VF dose. If the subject requires further assistance this will be provided (i.e. it is not mandatory that these infusions are performed at home).
- There will be a telephone follow up by an appropriately qualified site staff member on day 3 after each site administered and home administered infusion to check for any adverse reactions including infusion site reactions and remind subjects to document these in their subject study diary. The date of infusion is considered to be Day 0. If Day 3 is to fall on a weekend or public holiday then this telephone follow up call should be performed on the closest working day after Day 3 as possible.
- The subject will return to the clinic every four weeks for a safety assessment (hematology, chemistry, pre and post dose vital signs and physical exam). Their regular Subgam-VF infusion will be given whilst the subject is at the clinic and additional Subgam-VF vials will be dispensed. IgG trough levels will also be measured at the clinic visit every four weeks.
- PK sampling This will occur on Week 21 (defined as Steady State Day 0 to 7), and will continue over the subsequent seven days to allow calculation of AUC (see the PK schedule, Table 3, Appendix IV). If the PK sampling cannot be completed at Week 21 (eg. due to patients work/vacation schedule) then this can be delayed to start at Week 22, 23, 24 or 25; however, the patient should still visit the office/hospital for their week 21 infusion and complete the other assessments scheduled for Visit 8, if possible. Week 22 assessments (Visit 9) will normally coincide with the PK sampling Day 7. However, if PK sampling is delayed, Visit 9 will also be delayed. All PK blood samples will be taken at the study site. However, if an appropriately qualified member of the study team is available, arrangements to collect the remaining PK samples from Steady State Day 1 onwards at the subject's home could be made, to help reduce the number of visits to the sites. Alternatively a Home Health Agency may be utilized to take the PK samples outside of the investigational site.

- In exceptional circumstances, and with prior Sponsor approval, if one of the following PK samples if lost, unevaluable, or not taken it may be taken at the same timepoint during the week following the PK assessment, as long as the same dose in mg/kg has been given:
  - $\circ$  1 day (24 hours  $\pm$  2 hours)
  - $\circ$  2 days (48 hours  $\pm$  4 hours)
  - $\circ$  3 days (72 hours  $\pm$  6 hours)
  - $\circ$  5 days (120 hours  $\pm$  8 hours).

# Follow-up visit and end of study

- Follow-up visit (Week 27) A follow up visit will occur seven days (+/- 1 day) after the last Subgam-VF infusion has been completed, to carry out assessments for safety. Blood samples will be taken at this visit. This visit must occur prior to administration of a new IgG product.
- Telephone follow-up (Week 30) 28 days (+/- 1 day) after the last Subgam-VF infusion the subject will be contacted by the site via the telephone to check for any AEs.

It is expected that any given subject will complete all treatments and follow-up assessments within approximately 30 weeks, (26 weeks on Subgam-VF, plus four weeks follow-up). The end of the trial will be after the last subject's last visit (which will be the telephone follow-up (Week 30) visit for the last subject).

## 7.2. Infusions

Subjects will receive 26 infusions of Subgam-VF subcutaneously on a weekly schedule using the supplied infusion pumps.

## Rescheduling of Infusions (visit windows)

If absolutely necessary (e.g. because of unavoidable conflicts) Subgam-VF infusions can be rescheduled +/- 1 days. The reason why this visit was rescheduled should be recorded in the eCRF. If there is a deviation from the scheduled visit/ visit windows, the study monitor should be contacted, and the deviation must be documented appropriately. These circumstances must not become routine. If an infusion is rescheduled the other planned study assessments should also be rescheduled so that these are performed on the day of infusion.

If the infusion just prior to PK sampling has to be rescheduled, then the PK sampling should be postponed to ensure that the PK samples are collected seven days after the last Subgam-VF infusion and the sampling times in Table 3 are adhered to.

#### 7.3. Pharmacokinetics

All subjects will participate in the pharmacokinetic (PK) segment of the study (if blood withdrawal volumes allow), see Appendix IV, Table 3. In the case of younger subjects, pediatric blood volumes will need to be taken to ensure the maximum blood withdrawal volumes specified in Appendix V are adhered to (see Laboratory Manual for more details).

- In exceptional circumstances, and with prior Sponsor approval, if one of the following PK samples if lost, unevaluable, or not taken it may be taken at the same timepoint during the week following the PK assessment, as long as the same dose in mg/kg has been given:
  - $\circ$  1 day (24 hours  $\pm$  2 hours)
  - $\circ$  2 days (48 hours  $\pm$  4 hours)
  - $\circ$  3 days (72 hours  $\pm$  6 hours)
  - $\circ$  5 days (120 hours  $\pm$  8 hours).

Where possible, arrangements to collect PK samples at the subject's home, from Steady State Day 1 onwards, by a suitably qualified member of the study may be made.

IMPORTANT: If the infusion just prior to PK sampling has to be rescheduled, then the PK sampling should be postponed to ensure that the PK samples are collected seven days after the last Subgam-VF infusion and the sampling times in Table 3 are adhered to.

# 7.4. Clinical Laboratory Tests

All blood samples collected for the study will be processed by a central laboratory. Once the results are made available, eligibility should be checked by the Investigator and eligible subjects may be enrolled into the study.

Samples for clinical laboratory testing should be taken before certain infusions, unless otherwise indicated, as per the Schedule of Assessments (Appendix IV Table 2) and will include:

- Biochemistry –including: alanine aminotransferase (ALT), aspartate aminotransferase (AST), creatinine, blood urea nitrogen (BUN), lactate dehydrogenase (LDH), sodium, potassium, total bilirubin, alkaline phosphatase, glucose and gamma-glutamyl transpeptidase (GGT).
- Hematology Complete Blood Count (CBC) with differential including: hematocrit, hemoglobin, red blood cells (RBC), platelet count and white blood cells (neutrophils, lymphocytes, monocytes, eosinophils, and basophils).
- Tests for hemolysis

Page 25 of 87

- o Direct Coombs' Test (Direct Antiglobulin test DAT)
- o Haptoglobin
- o Plasma free hemoglobin
- Urine hemosiderin

Tests for bilirubin and serum LDH in the standard biochemistry panel is also considered a test for hemolysis.

- Specific antibody function to test for antibodies against the following antigens:
  - o Haemophilus influenzae B
  - o Streptococcus pneumoniae.
  - Measles
- Virology testing
  - Serological tests for HBsAg, HCV, HIV 1 & 2 at screening for eligibility and at Week 27 Follow up visit
  - o Nucleic Acid Testing (NAT) for HCV, HIV at Week 27 Follow up only
  - o Parvovirus B19 NAT and serology at Infusion 1, 2 and Week 27 Follow up visit.
- Urinalysis that will include microscopic examination.
- Pregnancy testing all females of child-bearing potential will receive a urine-based, human chorionic gonadotropin (HCG) pregnancy test regardless of claimed inability to conceive (including patients who have undergone surgical sterilization).

# 7.4.1. Effects on Hepatic, Renal, and Hematologic Function

If the results of any blood test demonstrate a rise to 2.5 times the upper limit of normal in AST, ALT, or bilirubin, these laboratory results will be documented as an AE.

A blood test demonstrating a change in renal or hematologic function will be documented as an AE if considered clinically significant by the Investigator.

# 7.4.2. Direct Coombs' Test

Blood samples for Direct Coombs' Tests and tests for hemolysis (bilirubin, haptoglobin, serum LDH, plasma free hemoglobin and urine hemosiderin) will be drawn at various times during the study (as detailed in Appendix IV, Table 2). Tests for bilirubin and LDH are included in the biochemistry panel.

In the event that a Direct Coombs' Test result is positive, the following procedures should be followed:

• The laboratory will notify the Investigator and the designated CRO within two business days of receiving the abnormal result.

Page 26 of 87

- Subjects with a positive result will be flagged by the laboratory, and those subjects will have a Direct Coombs' Test and other tests for hemolysis (as detailed above) before every subsequent infusion given during a clinic visit and at the follow-up visit.
- Upon receiving a first report of a positive direct Coombs' test on any subject, the Investigator will contact the subject to return for additional laboratory testing for haptoglobin, serum LDH, plasma free hemoglobin bilirubin, and urine hemosiderin as soon as practically possible (generally within three business days) and will assess the subject in order to determine if there is any clinically significant hemolysis. Thereafter, further tests for hemolysis may be done if clinically indicated and at the discretion of the investigator.
- All positive Direct Coombs' tests will be reported as adverse events.

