# 13.4. Safety Analysis

#### 13.4.1. Adverse Events

Summaries of AEs will be based on treatment-emergent AEs (TEAEs), defined as those events with onset date between the first infusion date and 28 days after the last infusion.

The number and percent of infusions associated with one or more AEs (irrespective of causality) that occur during the infusion or within 72 hours after completion of the infusion will be calculated. A 1-sided 95% upper confidence bound for this percent will be derived. If the upper bound is less than 40%, excluding local infusion site reactions, the incidence of infusion-related AEs associated with Subgam-VF will be considered acceptable. In addition, the number and percent of subjects who report any AEs and the number and percent of subjects who report any AEs at least possibly related to Subgam-VF will be calculated, and the upper bound of the 95% confidence interval for the percentages will be presented. AEs occurring during the infusion and within 1, 24, 48 and 72 hours after the infusion completion will also be summarized.

An adverse reaction will be defined as any AE occurring during the infusion and within 72 hours after the infusion completion OR any AE classed as product-related or with unknown causality.

AEs that occur during an infusion will be summarized by the infusion rate at which the AEs are reported. If necessary, infusion rates will be grouped into different levels.

SAEs and SUSARs will be summarized with all AEs, and separate listings will be provided for SAEs and SUSARs.

All other safety assessments will be summarized descriptively for each treatment group.

Further summaries of AEs will be detailed in the Statistical Analysis Plan.

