## **APPENDIX IV- VISIT SCHEDULE**

**Table 2 Schedule of Assessments** 

Assessment																		
(Wk)	Screen	1 a	2	3 to 4	5	6 to 8	9	10 to 12	13	14 to 16	17	18 to 20	21	22	23 to 25	26	27 FU b	30 Telephone FU c
Clinic Visit No.	1	2	3		4		5		6		7		8	9		10	11	
Informed Consent	X																	
Inclusion /Exclusion Criteria / Eligibility	X	X																
Medical History	X																	
Physical Examination	X	X							X								X	
Weight	X	X	X		X		X		X		X		X	X		X	X	
Chest X-ray – if not available in previous 12 months		X																
Vital signs d	X	X	X		X		X		X		X		X	X		X	X	
Infusion with Subgam-VF		X	X	X	X	X	X	X	X	X	X	X	X	X	X	X		
Infusion Site Inspection for reactions		X	X	X	X	X	X	X	X	X	X	X	X	X	X	X		
Concomitant medications	X	X	X	X	X	X	X	X	X	X	X	X	X	X	X	X	X	X
Adverse event reporting e	X	X	X	X	X	X	X	X	X	X	X	X	X	X	X	X	X	X
TEE examination f	X																X	
Hematology	X	X	X		X		X				X						X	
Biochemistry	X	X	X		X		X				X						X	
Urinalysis	X	X									X						X	
HCG urine pregnancy test	X																	
IgG trough levels	X	X	X		X		X		X		X		X	X		X	X	
IgA, IgM g	X																	
IgG subclasses	X																X	
Specific anti-bodies h	X																X	

Page 83 of 87

Bio Products Laboratory Ltd. CONFIDENTIAL

Assessment																		
(Wk)	Screen	1ª	2	3 to 4	5	6 to 8	9	10 to 12	13	14 to 16	17	18 to 20	21	22	23 to 25	26	27 FU b	30 Telephone FU c
Clinic Visit No.	1	2	3		4		5		6		7		8	9		10	11	
Virology i	X																X	
Parvovirus B19 j		X	X														X	
Direct Coombs' Test k		X	X						X								X	
Haptoglobin, plasma free hemoglobin, urine hemosiderin 		X	X						X								X	
PK assessment m													X	X				
Study Diary issue	X	X	X	X	X	X	X	X	X	X	X	X	X	X	X	X		
Reserve sample	X	X	X		X		X		X		X		X	X		X	X	
Archive: Store at –70°C for 15 years		X															X n	

- Eligible subjects return 7 days (+/- 1 day) for their first Subgam-VF dose. Infusion visits will be scheduled every 7 days. Individual infusions may be administered at ± 1 day of the planned schedule, if absolutely necessary (e.g. because of unavoidable conflicts, see section 7.2 for details)
- Week 27 Follow-up visit will occur seven days (+/- 1 day) after the last Subgam-VF infusion. This visit must occur prior to administration of a new IgG product.

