- Week 30 Telephone follow-up will occur 28 days (+/- 1 day) after the last Subgam-VF infusion to check for AEs.
- Vital signs will be recorded once during the screening and follow up visits. During Subgam-VF infusion site visits vital signs will be collected 10 minutes before the start of each infusion (+/- 5 minutes) and 30 minutes after stopping the infusion (+/- 15 minutes).
- e AEs will be documented from the date of consent until the last follow-up visit. AEs will be collected in subject diaries and by direct observation during each site visit. In addition there will be a telephone follow up by the site on day 3 after each infusion to check for any adverse reactions including infusion site reactions. The date of infusion is considered to be Day 0. If Day 3 is to fall on a weekend or public holiday then this telephone follow up call should be performed on the closest working day after Day 3 as possible.
- Thromboembolic event (TEE) monitoring to be performed at screening and at the follow-up visit- refer to section 7.8 for details
- IgA, IgM testing for IgA and IgM will only occur in those subjects where results are not available for the previous 12 months
- Specific anti-bodies for *Streptococcus pneumoniae* and *Haemophilus influenzae* B will be measured at screening and FU visit. Anti-bodies for measles will be measured at FU visit (this visit must occur prior to administration of a new IgG product as a trough sample is required).
- Virology Serological tests for HBsAg, HCV, HIV 1 & 2 performed at screening and Week 27 FU visit, NAT for HCV and HIV only performed at Week 27 FU visit.
- Parvovirus B19 PCR/NAT and serology
- Direct Coombs' Test and tests for hemolysis will be repeated for the subject at each subsequent clinic visit if the result is positive at any visit

Bio Products Laboratory Ltd. CONFIDENTIAL

- **Haptoglobin, plasma free hemoglobin, urine hemosiderin** tests for hemolysis will be repeated for the subject at each subsequent clinic visit if the result is positive at any visit

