10.1 Baseline Value

Unless otherwise specified, baseline is the last available observation before the start of the first infusion of study drug.

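### A positive Direct Coombs' test on the Week 1 pre-dose sample counts as a treatment-emergent adverse event, although it precedes any Subgam-VF exposure and is also the SAP baseline

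*Protocol*

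**What the plan says.** **Testing schedule.** In Protocol Appendix IV, Table 2, the row "Direct Coombs' Test k" (k is a footnote letter) is marked at Weeks 1, 2, 13 and 27. The screening cell is empty. Protocol 7.4 says "Samples for clinical laboratory testing should be taken before certain infusions, unless otherwise indicated, as per the Schedule of Assessments". At the screening visit, "subjects receive their usual dose of IGIV/SCIG and have all safety screening tests performed" (Protocol 7.1), and the first Subgam-VF dose follows 7 (+/- 1) days later.

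**Adverse event rule.** Protocol 7.4.2: "All positive Direct Coombs' tests will be reported as adverse events". After a positive, "tests for hemolysis will be repeated for the subject at each subsequent clinic visit if the result is positive at any visit" (Table 2 footnote).

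**TEAE rule.** Protocol 13.4.1 bases the summaries on TEAEs, "defined as those events with onset date between the first infusion date and 28 days after the last infusion". SAP 10.3 and 13.2 repeat this rule. None of the three uses clock time or requires the event to be new or worse than before treatment.

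**Baseline.** SAP 10.1: unless otherwise specified, "baseline is the last available observation before the start of the first infusion of study drug".

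**Presentation.** SAP 13.4 tabulates hemolysis markers, including the Coombs' result, by visit, and lists Coombs' results with hemoglobin change at each visit. The only shift table in that section is for the viral tests.

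**The concern.** Describing the adverse events of Subgam-VF is a secondary objective. Read together, the rules above let a result obtained at zero exposure enter the table that answers it, and one observation serves both as baseline and as an on-treatment event.

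Related rules in the protocol do ask for a change. Virology acts on a change in viral status and rechecks a reserve sample from before the first infusion (7.4.3). Physical examination findings become adverse events on a clinically significant change from baseline (7.7). The other hemolysis criteria in 7.4.2 rest on falls and rises, with LDH compared with baseline. The Coombs' rule has no such condition.

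At stake are the all-causality TEAE incidence, the tables by system organ class and preferred term, and possibly the table of events seen in at least 5% of subjects.

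**Working it through.** The documents state no rate or power for Coombs' positives, so there is no planned figure to reproduce. The power statement in Protocol 13.1 concerns exposure and plays no part here.

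**Step 1: is the first test before exposure?** There is no screening test (Table 2), and samples are taken before the infusion (7.4) on the infusion day (7.2). The first result therefore comes from a sample drawn 7 - 1 = 6 to 7 + 1 = 8 days after the screening visit, before any Subgam-VF.

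**Step 2: apply the TEAE rule.** Take a sample 30 minutes before the first infusion (an illustrative time; any earlier time that day gives the same answer).
- Date rule: onset day 0 is not before first infusion day 0, so the event is a TEAE.
- Date-and-time rule: onset -0.5 h is before 0 h, so it is not.

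**Step 3: compare with the baseline rule.** The same sample is the last observation before the first infusion, so it is the baseline under SAP 10.1. The TEAE rule makes no use of baseline.

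**Step 4: which outputs change?**
- All-causality TEAE incidence and the tables by system organ class and preferred term: yes.
- TEAEs by most recent infusion number, and by hours since infusion completion (SAP 13.2): a pre-dose event has no preceding infusion and fits no category.
- Product-related tables: no, if rated unrelated.
- FDA-specified adverse reaction table: no, if rated unrelated. It needs onset during or within 72 hours after an infusion, relatedness, or missing or indeterminate causality.
- The 40% infusion criterion: no, with onset at the sample time. The event precedes the infusion, and later scheduled pre-dose samples come about 7 days (168 h) after the previous infusion, beyond 72 h. Even if one event were wrongly assigned to the first infusion, it would change 1 of 30 x 26 = 780 infusions, or 0.13 percentage points.

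**Step 5: size.** Each affected subject adds 1/N to the subject incidence of that event: 1/30 = 3.3 points, 1/50 = 2.0 points (30 evaluable, up to 50 enrolled; Protocol 13.1).

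The share p of subjects positive before dosing is not in the documents. As an assumption with a range, expected affected subjects = Np, and P(at least one) = 1 - (1 - p)^N. Entry to the table of events in at least 5% of subjects needs 0.05 x 30 = 1.5, so 2 subjects, or 0.05 x 50 = 2.5, so 3. The last column is the binomial chance that pre-dose positives alone reach that number.

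| N | assumed p | expected subjects | P(at least one) | P(enters 5% table) |
|---|---|---|---|---|
| 30 | 1% | 0.3 | 26% | 3.6% |
| 30 | 5% | 1.5 | 79% | 44.6% |
| 30 | 10% | 3.0 | 96% | 81.6% |
| 50 | 1% | 0.5 | 39% | 1.4% |
| 50 | 5% | 2.5 | 92% | 45.9% |
| 50 | 10% | 5.0 | >99% | 88.8% |

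At the threshold the table would report 2/30 = 6.7% (exact 95% CI 0.8 to 22.1) or 3/50 = 6.0% (1.3 to 16.5), with no product effect at all.

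**The case against.** The other side has good points.

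- **Causality assessment separates most of it.** Appendix I, 2.1 includes an incompatible time relationship in its definition of unrelated, and a pre-dose finding meets that. This stands, and limits the problem to the all-causality tables.
- **The result is visible anyway.** The by-visit table and listing in SAP 13.4 would show a Week 1 positive. This stands, but it does not correct the TEAE count.
- **Onset date is not fixed.** No rule sets the onset date of a laboratory adverse event, and an investigator could date it earlier. This stands as a condition: the point applies when onset is dated to the sample. Nothing directs sites to do otherwise.
- **The rule errs towards over-reporting.** True, and no safety decision changes.

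A reader might also infer more than the documents support.

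- **Ten adverse events from one subject.** A Week 1 positive leads to retests at Weeks 2, 5, 9, 13, 17, 21, 22, 26 and 27, so ten tests in all. Section 7.4.2 does not say that each repeat of a persisting positive is a new event. The record holds start and stop dates, so one open record fits. Repeats could raise the event count but not the subject percentage. What stands is that the counting is unspecified.
- **Carry-over from the previous IgG product.** The sequence of doses makes this tempting, but the documents do not say that prior IgG causes positives. A positive from any pre-existing cause is enough.
- **All Week 1 laboratory findings.** Other laboratory adverse events mostly need clinical significance or change (Protocol 7.4.1; Appendix I, 1.1), and hematology, biochemistry and urinalysis have a screening value. The exposure is largely confined to the Coombs' test.

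**Conclusion.** The point holds in a limited form. It is a stated rule that gives a wrong count, not a missing detail: a Week 1 pre-dose positive dated to its sample is tabulated as treatment-emergent and is also the baseline. The size is 3.3 percentage points per affected subject at N = 30 and 2.0 at N = 50, on the subject incidence of that event.

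This rests on three assumptions: samples are drawn before dosing as Protocol 7.4 directs, onset is dated to the sample, and at least one subject is positive beforehand. The documents do not support any particular frequency; the 1% to 10% range only illustrates.

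It should be corrected before database lock because the correction is cheap. It does not put the 40% criterion in doubt.

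**What to change.** 1. In Protocol 13.4.1 and SAP 10.3 and 13.2, define a TEAE as an adverse event with onset date and time at or after the start of the first Subgam-VF infusion, or one that worsens after it.
2. Add a missing-time convention: an event on the first infusion date with no onset time counts as a TEAE unless it comes from a sample documented as pre-dose. This is needed because Appendix I, 2.1 records date and time, Appendix I, 1.1 lists only a date, and SAP 10.2 imputes nothing.
3. Treat the Week 1 pre-dose Coombs' result as baseline and list a positive there as pre-treatment.
4. Count a later positive as a TEAE when it follows a negative result, or when the Week 1 result is missing. Count an uninterrupted persistent positive as one event. Requiring a negative Week 1 result instead would lose subjects with no Week 1 test and those who go from positive to negative and back to positive on treatment.
5. Add a baseline to post-baseline Coombs' shift table to SAP 13.4.

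All positives remain reported and listed, and the follow-up in Protocol 7.4.2 is unchanged. The cost is wording in both documents, a short missing-time convention and one more table. No new test is needed.
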